We are able to create constructs such as active life expectancy [e.g. Manton, 2008], healthy life expectancies [Molla, 2008], disability-free life expectancy [Andrade, 2010], and multimorbidity transition rates [Kadam, 2013] that can expand the exploration of long-term intervention effects on novel outcomes.

5.8 Study Monitoring.

The progress of LA-E and the study's potential of attaining its goals will be regularly evaluated by the Data and Safety Monitoring Board (DSMB). This committee will review and provide feedback to the NIDDK on the overall performance of the study group, including its success with respect to goals for recruitment, retention, safety, and data quality.

Recruitment and retention We will provide summary data on re-enrollment in terms of number of informed consent documents signed for each site and overall. Retention will be monitored continuously throughout LA-E. We will provide summary data on failure to obtain required exams/follow-up visits on time and the number of consent withdrawal and inability to contact the participants for each site and overall. These summary data will also be presented to the DSMB committee by intervention assignment and by age group. This will assure early recognition of inadequate performance and identify reasons for inadequate performance in each clinical site and in the study overall.

Safety Two types of safety events will be reported in LA- E. The first type that will be reported are events or problems that are unexpected or unanticipated; and possibly, probably, or definitely related to participation in the study; and are fatal, life threatening, or serious. An example of this would be an accident that happened in the clinic such as a serious fall. The second type that will be reported are events or problems that may not be serious but are events or problems that are unexpected or unanticipated; and possibly, probably, or definitely related to participation in the study and not serious, but suggest greater risk or harm to study participants than was previously known or recognized. Examples of this would include a Breach of Confidentiality or information that indicates a change to the risks or benefits of participating in the study.

We will summarize all adverse event (AEs) and serious adverse events (SAEs) for each system organ class by intervention assignment and CVD history. The number of participants and percentage reporting an event will be compared between DSE and ILI using either chi-square tests or Fisher's exact tests (when expected cell counts are small). The incidence rates of an event between DSE and ILI will be compared using likelihood ratio method. At each DSMB meeting, the committee will review data on adverse events and other safety issues to make an overall recommendation to the NIH concerning the safety of continuing LA-E. Consistent with NIH policy, each LA-E Principal Investigator will receive a report summarizing the DSMB review of the adverse event data. Principal Investigators are responsible for providing this report to the IRB at their institution.

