In addition to the above procedures related to the capacity to consent, participants will be asked to consent to having their Protected Health information shared with and electronically transferred to the coordinating center at Wake Forest School of Medicine. Participants are not required to consent to this sharing of information; their decision not to share this information will not affect their participation in the Look AHEAD Extension. However, if provided, this shared information will be used at the coordinating center in the event of natural or other major disaster affecting a clinical site (for example, if a clinic were destroyed by a hurricane or tornado, the coordinating center would be able to provide contact information for the participant to the clinics). Also, the information would be used to allow searches of national databases such as the National Death Index (NDI) or Centers for Medicare and Medicaid Services (CMS) for the purpose of determining date and cause of death, and diagnosis codes and dates for health care utilization. These would require that the coordinating center have access to names, addresses, birth dates, social security number, and/or Medicare number. In addition, in the event that future funding is not available for the clinics to contact their participants, this information would be used to allow direct contact by the coordinating center with the participant, by telephone or mail, for the following purposes: to invite the participant to take part in an ancillary study; to conduct the study outcomes interview; to conduct other types of interviews, e.g., to inquire about current health status, body weight, and to update contact information on informants/proxies.

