1.4 OUTCOMES

1.4.1 Primary Outcomes

The co-primary outcomes for Look AHEAD Extension are lifespan, and health care costs

Lifespan will be measured by all-cause mortality from the time of randomization and is determined at a six-month interval through telephone contact with the participant, or through family members or obituaries. In addition, a National Death Index search will be conducted at several time points during the Look AHEAD Extension. Cause-specific mortality (a supporting analysis) will be determined through adjudication of death certificates, recent hospitalization

records (discharge summaries only), and previous outcomes interviews. These records will be sent to the coordinating center for processing, and a central adjudication committee (study investigators/physicians) will meet by conference call to adjudicate deaths for the purpose of determining cause-specific deaths, using procedures currently in place for Look AHEAD.

Health care costs will be assessed post-intervention from the perspective of the payer. Costs will be calculated from hospitalization records (medical coded discharge summaries), outpatient visits (office, hospital clinic, other), outpatient tests and procedures, rehabilitation/long-term care, home care, and medications identified at the six-month telephone contacts and biennial clinic visits. Supporting analyses will include measures of health care utilization: hospitalizations and days hospitalized, medication use, nursing home residences. The Look AHEAD Extension will also report separately costs for each of the major components of total costs.

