1.0 Introduction and Background

The Action for Health in Diabetes Extension (LA-E) builds on the success of Look AHEAD (LA) in producing and maintaining significant differences in weight loss over 10 years in participants who were randomly assigned to intensive lifestyle intervention (ILI) or its comparison condition of diabetes support and education (DSE). Even though the lifestyle intervention in LA ended in September 2012 due to futility in the primary outcome (fatal and non-fatal myocardial infarction and stroke, hospitalization for angina), follow-up continues into the post-intervention phase of the trial – the Look AHEAD Continuation (LA-C) – through the end of 2015. We continue to observe legacy effects of the intervention on many health outcomes related to diabetes and aging. Of the original randomized 5145 participants, we anticipate following 3800 participants in LA-E (i.e. over 80% of the surviving cohort and 96% of those currently active). We propose to follow these participants with biennial clinic visits and 6-month outcomes phone calls through 4.5 years.

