When repeated outcomes are available, continuous outcomes will be analyzed using linear mixed effects models to estimate the intervention effects. Count data (e.g., number of hospitalizations) will be analyzed using Poisson or negative-binomial regression, for which the natural log of the follow-up time will be included in models as an offset term. Generalized linear models, including generalized estimating equations (GEE) for repeated measures, will be used to analyze binary outcomes with a logit link function.

For each specific aim, we clearly identify the timeframe for analyses.

- For some outcomes (e.g. mortality, renal replacement therapy) inference involves data collected through the full span of LA, LA-C, and LA-E follow-up. It is necessary to have the full span of follow-up to have adequate power for these outcomes. We will, in supporting analyses, estimate intervention effects during the intervention phase and post-intervention phases of follow-up, but the primary comparisons will span these two time periods.

- Other outcomes (e.g. costs, SF-36) have been featured in publications from the intervention phase of the trial (prior to 9/2012 in LA). For these, LA-E aims and principal inferences are based on data collected post-intervention and we project to have sufficient power for these comparisons. In supporting analyses, we will also portray data by intervention assignment from the time of randomization, but this will be for descriptive purposes.
- Some outcomes (e.g. frailty) have not been measured previously in LA , so that inference is based solely on LA-E data.

In projecting statistical power, we have made the following assumptions. For mortality, we have assumed that the percentage of individuals who we are unable to track with respect to mortality would accrue at 1%/yr. We have also assumed that the inability to establish mortality status on participants who were actively followed will also additionally accrue at 1%/yr. For general data collection, we assume that lost follow-up will accrue at 2%/yr (note that throughout the first 12 years of LA, lost follow-up accrued at 1.2%/yr). We also project that we will continue to obtain clinic-based measures on >95% of participants who are currently active (i.e. who are not lost to follow-up for general data collection).

4.4 Missing data.

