5.0 Analytical Plan For Specific Aims

5.1 Specific Aim 1 (primary) is to test the hypothesis: The hazard rates for total mortality will differ between intervention groups across follow-up. Mortality will be adjudicated from death certificates, recent hospitalization records (discharge summaries only), outcomes interviews, and National Death Index (NDI) search. All data collected since randomization will be included. Time to death from any cause will be measured from the time of randomization. Follow-up time for participants who remain event free will be calculated as the time in years from randomization to their last available visit. The primary analysis of the all-cause mortality will be proportional hazards regression with stratification for clinical sites, mirroring the analysis of the trial's primary composite cardiovascular disease outcome. Significance for the intervention effect will be based on the likelihood ratio test. Hazard ratio (HR) and 95% confidence intervals will be constructed from the fitted models. The proportional hazard assumption will be examined using log/log plots of survival [e.g. Lagakos, 1984] and alternative models may be used as sensitivity analyses, if necessary. For example, we have experience in applying parametric Weibull models [Lawless, 2003] to the LA mortality data. In addition, Kaplan-Meier plots will be used to present the survival curves by intervention.

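### Mortality counts deaths found without attendance but censors survivors at their last visit, so absolute mortality is overstated in both arms

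*Combined protocol and SAP*

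**What the plan says.** SAP 5.1 and Protocol 1.5 describe the mortality analysis in the same terms.

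- **Deaths.** They come from death certificates, hospital discharge summaries, "outcomes interviews, and National Death Index (NDI) search". "All data collected since randomization will be included". Protocol 1.4.1 says that status is obtained every six months "through telephone contact with the participant, or through family members or obituaries", and that "a National Death Index search will be conducted at several time points during the Look AHEAD Extension".
- **Survivors.** "Follow-up time for participants who remain event free will be calculated as the time in years from randomization to their last available visit".
- **Limit on the search.** Protocol 1.3.4 links NDI searching to the transfer of identifiers to the coordinating center, and "Participants are not required to consent to this sharing of information". No consent or linkage rate is given.
- **Loss.** SAP 4.3 assumes that general follow-up is lost at 2% per year (1.2% per year over the first 12 years). Separately, it assumes that "the percentage of individuals who we are unable to track with respect to mortality would accrue at 1%/yr". The power paragraph of SAP 5.1 also uses 1% per year for vital status.
- **Dropout.** SAP 4.4 plans inverse probability weighting for survival outcomes, as a sensitivity analysis.

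I found no closing date for the NDI search, no definition of *visit*, and no rule that excludes a death after last contact.

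**The concern.** The two halves of the rule use different clocks. A death is counted whether or not the person still attends, while time alive is credited only up to the last attendance. Take two people who leave contact in year 8. One dies in year 14 and is found in the NDI: this person contributes 14 years and an event. The other is alive in 2020 and contributes 8 years. Membership of the risk set after year 8 then depends on the later outcome, which breaks the non-informative censoring that Cox and Kaplan-Meier estimates need.

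The plan implies that such people exist. It assumes general loss of 2% per year against 1% per year for unknown vital status, so it expects to know the status of some who have left. (SAP 4.3 adds a further 1% per year for unestablished status among those actively followed, so the size of that group is uncertain.)

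At stake are the planned Kaplan-Meier curves and cause-specific rates, and the SAP 5.1 comparison of hazard rates between the intervention and post-intervention phases. If loss or linkage came to differ by arm, the hazard ratio would be affected too.

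**Working it through.** **The plan's own figures.** The plan gives no mortality figure under this rule. The nearest anchor is 509 projected DSE deaths by 7/2020. "Of the original randomized 5145 participants", allocated 1:1, half is 5,145/2 ≈ 2,573, and 509/2,573 = 19.8%. The 88% conditional power cannot be reproduced uniquely because deaths to date are not stated. This point does not test it.

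**Assumptions not in the documents.** Weibull mortality with shape 2 and 20% dead at 17.5 years; administrative end 16.2 to 18.9 years after randomization; loss independent of death; NDI linkage varied. From the documents: loss of 1.2% per year and six-monthly contacts.

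**True 16-year mortality.** Cumulative hazard H(16) = −ln(0.80) × (16/17.5)² = 0.2231 × 0.836 = 0.1865. Mortality = 1 − exp(−0.1865) = 17.0%.

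**Inflation of the hazard.** Let e = exp(−0.012t) be the share still in contact, p the share of leavers who can be linked, and q the probability that someone alive at t dies before the end of follow-up. Under the rule as written, the hazard at t is multiplied by

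[e + p(1 − e)] / [e + p(1 − e)q].

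At t = 16, with the end at 17.5 years: e = 0.825 and q = 1 − 0.800/0.830 = 0.036.

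- p = 1: 1/(0.825 + 0.175 × 0.036) = 1/0.832 = 1.20
- p = 0.5: 0.913/0.828 = 1.10
- p = 0: 1.00

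At t = 10 with p = 1: e = 0.887 and q = 0.140, giving 1/(0.887 + 0.113 × 0.140) = 1/0.903 = 1.11. The inflation grows with time. Integrating the inflated hazard to 16 years with p = 1 gives a cumulative hazard of 0.209, and 1 − exp(−0.209) = 18.9%.

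**Simulation, 600,000 per arm, same assumptions:**

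| Who can be linked | DSE 16-year mortality as read | True |
|---|---|---|
| Only those in contact at Extension start (2/2016, 4.4 years before 7/2020) | about 17.2% | 17.0% |
| 50% at random | about 18% | 17.0% |
| Everyone | 18.9% | 17.0% |

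A second calibration, to 509 ascertained DSE deaths with loss of 1.2% and then 2% per year, gives 18.7% against 16.7% with full linkage, and 19.0% against 17.9% with 50% linkage. With full linkage, loss of 1% per year throughout gives 18.2% and loss of 2% throughout gives 19.9%, both against 16.7%.

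**Late-phase rates.** With full linkage and loss of 1.2% then 2% per year, the DSE rate is inflated by about 5% before year 10 and by about 22% after it (24.3 against 20.0 per 1,000 person-years).

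**Hazard ratio.**

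- Balanced loss, second calibration: 0.805 under the rule against 0.803 with the true follow-up. A null HR stays at 1.00.
- Unequal loss, full linkage, 1.0% per year in ILI and 1.4% in DSE (assumed): at t = 16 the inflation denominators are 0.852 + 0.148 × 0.036 = 0.857 and 0.799 + 0.201 × 0.036 = 0.807, a ratio of 0.94. Over all follow-up a null HR reads 0.96. With 2 × 509 = 1,018 deaths the shift in Z is about 0.041 × √(1,018/4) = 0.65, against the planned critical value of 2.6.
- The same unequal loss gives a null HR of about 0.98 with 50% linkage, and about 1.00 if only people in contact at Extension start are searched.

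**The case against.** **The primary inference is a hazard ratio.** SAP 5.1 tests it with a likelihood ratio test. Protocol 1.3.3 and SAP 4.2 and 4.4 describe retention as similar or balanced between arms. With equal loss the inflation cancels almost exactly. This stands.

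***Visit* probably includes the telephone calls.** Protocol 1.4.1 sets six-monthly contact for vital status, and Table 1 lists mortality under the six-month calls. SAP 5.4 applies the mortality method to ESRD and says that times cluster at six-month points, dated by participant encounter. This stands: a reader might take *visit* to mean the biennial clinic exam and infer a much larger error in the tail, but the documents point the other way.

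**Full linkage is an extreme.** Sharing identifiers is optional, and the request described is made of Extension participants. The 3,800 expected are over 80% of survivors, so there are fewer than 3,800/0.80 = 4,750 survivors and fewer than 950 outside the Extension. Whether earlier consents cover those people is not stated. This stands, and it is why the size is given as a range that starts near zero.

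**Safeguards exist.** Dropout patterns will be compared by arm, retention goes to the DSMB by arm, and inverse probability weighting is planned. These would help to reveal unequal loss. They do not cure the defect: the weighting is only a sensitivity analysis and leaves the censoring date unchanged.

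**Conclusion.** As written, the rule makes time at risk depend on the outcome. It overstates absolute mortality, the Kaplan-Meier curves and late hazard rates in both arms. The direction is clear whenever some people who have left contact can still be found dead. The size is not: at 16 years in DSE it runs from about 0.2 to 1.9 percentage points on a true 17.0%. That range rests on loss of 1.2% per year, six-monthly contacts, the assumed Weibull curve and administrative end, and unknown NDI linkage.

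A reader might infer that the treatment effect is biased. The documents do not support that: with balanced loss and linkage the HR is essentially unchanged, and retention is reported as balanced to date. The null HR of 0.96 is the largest shift among the cases run, and it needs both full linkage and a difference in loss that the documents do not report. Nor does this point show that the stated power is wrong.

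The rule should still be corrected before analysis, because it governs a co-primary outcome and the HR's protection depends on a balance that the plan cannot guarantee.

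**What to change.** In SAP 5.1 and Protocol 1.5:

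1. Censor event-free participants who were searched in the NDI at the closing date of the final search, not later than 7/2020.
2. Censor participants who cannot be searched at the last contact, phone included, that confirmed vital status. Count their deaths only through that contact schedule.
3. Define searched by consent and available identifiers, not by suspicion that the person has died, which would bring the asymmetry back.
4. Report the number searched and the loss to contact by arm.
5. Keep last-visit censoring as a sensitivity analysis.

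In the second calibration, censoring searched survivors at the closing date and the rest at last contact restored the true 16-year DSE mortality (16.7% with full linkage, 17.9% with 50% linkage) and gave an HR of 0.803 in both cases.

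The cost is wording in two places and some programming. The NDI search is already planned and need not be widened. The drawback is that searched and unsearched participants have separate censoring rules, which the report must explain.

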Action for Health in Diabetes (Look AHEAD, 2000-2012) was a 2-arm randomized, controlled multicenter clinical trial to examine whether an intensive lifestyle intervention (ILI) designed to achieve and maintain weight loss of at least 7% by focusing on reduced caloric intake and increased physical activity could reduce cardiovascular morbidity and mortality compared with Diabetes Support and Education (DSE), a standard care control group. Look AHEAD enrolled 5,145 overweight or obese volunteers with type 2 diabetes, with a planned follow-up period of up to 13.5 years. At randomization, the Look AHEAD cohort was comprised of 60% females, 37% minorities, mean age of 59.7 years (range: 45-76 years), and mean BMI of 35.9 kg/m²; the mean duration of diabetes was 5 years and 14% had a prior history of CVD at baseline. The primary endpoint was the first occurrence of a composite cardiovascular outcome that included death from cardiovascular causes, nonfatal myocardial infarction, nonfatal stroke, and hospitalized angina with a targeted between-group difference of 18% reduction in the composite endpoint in ILI vs. DSE. Three composite cardiovascular outcomes were also examined: 1) death from cardiovascular causes, nonfatal myocardial infarction, or nonfatal stroke; 2) death from any cause, myocardial infarction, stroke, or hospitalization for angina; and 3) death from any cause, myocardial infarction, stroke,

[figure not shown]

coronary-artery bypass grafting, percutaneous coronary intervention, hospitalization for heart failure, or peripheral vascular disease.

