Subgroup analyses: Pre-specified subgroup comparisons include sex, history of cardiovascular disease, race/ethnicity, and age. We will report tests of interactions to assess the consistency of differences between intervention groups for each of these subgroups.

Power: Because total mortality has been monitored over time and was selected from among a larger set of events contributing to the LA primary and secondary composite outcomes, some adjustment of the type 1 error should be made to avoid making a spurious claim on the effect of ILI on death rates. A conditional power calculation that uses the number of deaths in the DSE cohort as a measure of information is equivalent to treating LA as an events-driven study of total mortality. Based on the current mortality rate and the assumptions on follow-up rates (Section 4.3), we project that we will ascertain 509 deaths in the DSE arm by 7/2020 (date of the last LA-E contact). These projections take into account the increasing hazard of mortality and the expectations that 3800 participants will agree to be followed when LA-E begins in February of 2016 and that vital status will become permanently unknown on 1% of the cohort per year. In this conditional power calculation, we have assumed that the final critical value for testing the intervention effect will be 2.6, corresponding to a nominal p-value of 0.01, instead of 1.96 (i.e. the common unadjusted two-sided $\alpha=0.05$). This more conservative critical value tests the intervention effect with an adjustment for our history of testing for an intervention effect on total mortality since May of 2007 (at the request of the DSMB), as well as annual interim analyses during LA-E. The conditional power for a final p-value of 0.01 with a 20% intervention effect in future data is 88%.

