5.2 Specific Aim 2 (primary) is to test the hypothesis: the cumulative mean (discounted) total health care costs post-intervention will differ between intervention groups. As described in the protocol synopsis, health care costs during the intervention phase of the LA trial have been published [Espeland, 2104]. We have continued to collect these data post-intervention (i.e. after 9/2012) and Specific Aim 2 is based on these data as collected through 7/2020. Each participant's annual costs for hospitalizations, outpatient care, medications, and rehabilitation/nursing home stays will be tallied and divided by follow-up times to obtain observed costs per year. Weighted analysis of covariance will be used to compare intervention groups, with analytical weights proportional to participants' lengths of follow-up. Clinic, the sole stratification factor in randomization, will be used as a covariate. To accumulate costs post-intervention, annual estimates will be discounted at 3% per year and summed and bootstrapping will be used for confidence intervals of accumulated mean costs. We will also generate accumulated mean costs across the full span of follow-up (i.e. since randomization) for descriptive purposes.

Supporting analyses: We will also report whether differences in the separate components of health care costs (hospitalizations, inpatient, medications, other) differ between arms. Other supporting outcomes will be the annual rates of hospitalizations, medication use (by previously reported classes), nursing home stays, and rehabilitation center stays.

Subgroup analyses: Pre-specified subgroup comparisons include sex, history of cardiovascular disease, race/ethnicity, and age. We will report tests of interactions to assess the consistency of differences between intervention groups for each of these subgroups.

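### Both co-primary analyses adjust for clinic only; the tests are valid, but adding baseline age, sex and CVD history would probably gain modest precision, most simply in the cost model

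*Combined protocol and SAP*

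**What the plan says.** **Mortality (SAP 5.1, repeated in protocol 1.5).** "The primary analysis of the all-cause mortality will be proportional hazards regression with stratification for clinical sites". The stated reason is continuity: the model is used "with stratification for clinical sites, mirroring the analysis of the" original trial's primary cardiovascular outcome. No covariate beyond site is named.

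**Costs (SAP 5.2, repeated in protocol 1.5).** The comparison is a weighted analysis of covariance. "Clinic, the sole stratification factor in randomization, will be used as a covariate".

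**Where the prognostic factors appear.** Under both aims, "Pre-specified subgroup comparisons include sex, history of cardiovascular disease, race/ethnicity, and age". They enter only through interaction tests. Protocol 1.1 describes the cohort at randomization: "mean age of 59.7 years (range: 45-76 years"), 60% female, 14% with prior CVD.

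**Covariates elsewhere in the SAP.** Section 4.3 allows covariates in survival models generally but selects none for mortality. Section 4.4 adds predictors of missingness, as sensitivity analyses only. Lower-ranked outcomes get more than clinic: sex for frailty and persistent mobility disability (5.3), and baseline eGFR and baseline neuropathy status for those two outcomes (5.4).

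**The mortality hurdle (SAP 5.1, Power).** "we have assumed that the final critical value for testing the intervention effect will be 2.6, corresponding to a nominal p-value of 0.01". "The conditional power for a final p-value of 0.01 with a 20% intervention effect in future data is 88" per cent.

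**The concern.** Sample size and follow-up are fixed, so the remaining scope for gaining information lies in the analysis. Baseline covariates that predict the outcome can help in two ways:

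- In the linear cost model they remove explainable variance from the error term, which lowers the standard error and leaves the mean difference being estimated unchanged.
- In a Cox model, leaving out prognostic factors pulls the hazard ratio (HR) towards 1 while its standard error barely moves, so the test statistic shrinks.

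The three factors are already held and already named in the SAP. Secondary and supporting outcomes are adjusted for sex or baseline values, but the two co-primary outcomes are not. The only reason given, mirroring the earlier cardiovascular model, applies to mortality and not to costs. At stake is some power on each co-primary outcome, with mortality facing a critical value of 2.6.

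**Working it through.** **1. Costs: reproduce the plan's figure.** SAP 5.2 gives SE = $196/yr, two-sided alpha 0.05 and 80% power. Detectable difference = SE × (1.960 + 0.842) = 196 × 2.8016 = $549, as stated.

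**2. Costs: effect of adjustment.** If the added covariates explain a share R² of the residual variance, SE becomes 196 × √(1 − R²). The documents give no R², so 5%-15% is assumed. Power is taken at the $595/yr difference that SAP 5.2 cites from the intervention phase: Φ(595/SE − 1.96).

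| R² (assumed) | SE ($/yr) | Detectable at 80% | 595/SE | Power at $595 |
|---|---|---|---|---|
| 0 (planned) | 196 | $549 | 3.04 | 86% |
| 5% | 191 | $535 | 3.11 | 88% |
| 15% | 181 | $506 | 3.29 | 91% |

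**3. Mortality: the plan's 88%.** It cannot be fully reproduced, because current deaths by arm are not given.

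- *Unconditional power.* 509 DSE deaths with HR 0.80 throughout imply about 416 ILI deaths, 925 in total. The expected Z is ln(1/0.80) × √(925/4) = 3.39. Power is Φ(3.39 − 2.576) = 79% at two-sided 0.01. The stated 88% is therefore not the unconditional figure.
- *Conditional power.* SAP 4.2 reports a DSE excess of about 40 deaths. With exactly 40 and critical value 2.6, conditional power is 88% if DSE deaths so far are about 175, and 81% if they are 218. The figure 218 is a lower bound from SAP 1.0: 3,800 is over 80% of survivors, so there are fewer than 4,750 survivors and more than 395 deaths, and (395 + 40)/2 ≈ 218. With 218 deaths and an excess of 45 or 50, it is 86% or 91%. So 88% is attainable near the reported imbalance but can be neither confirmed nor refuted.

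**4. Mortality: effect of adjustment.** A site-stratified Cox model was simulated with and without age, sex and CVD history, 600 trials per scenario.

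- *From the documents:* N = 5,145, 1:1 within site, about 509 DSE deaths, 20% effect (taken as a covariate-conditional HR of 0.80), 1%/yr loss of vital status, critical value 2.6, baseline mix as in protocol 1.1.
- *Assumed:* 16 sites, age SD 6.8, Weibull shape 1.8, censoring at about 16-19 years, and the prognostic HRs below.

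Power is Φ(mean Z − 2.6).

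| Assumed prognostic HRs (per year of age / male / CVD) | HR, site only → adjusted | Mean Z | Power |
|---|---|---|---|
| 1.05 / 1.2 / 1.5 | 0.801 → 0.799 | 3.348 → 3.395 | 77.3% → 78.7% |
| 1.08 / 1.4 / 1.8 | 0.805 → 0.799 | 3.296 → 3.404 | 75.7% → 78.9% |
| 1.10 / 1.6 / 2.2 | 0.809 → 0.798 | 3.199 → 3.394 | 72.5% → 78.6% |

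The standard error of the log HR is about 0.066 in every cell. The gain of 1 to 6 points comes from less attenuation.

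**5. Translate to the stated 88%.** Z rises by 1.4% to 6.1% (3.395/3.348 and 3.394/3.199). Apply this to future data only, with information fraction t = 218/509 = 0.43 (the SAP measures information in DSE deaths). The future drift on the conditional scale is 3.39 × √(1 − 0.43) = 2.57, so the shift is 0.04 to 0.16. Starting from Φ⁻¹(0.88) = 1.175, conditional power becomes Φ(1.21) = 89% to Φ(1.33) = 91%. With t = 175/509 the rounded results are the same.

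**The case against.** The case for leaving the mortality model alone is substantial.

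- *Validity.* Randomization was 1:1 within center, and clinic was the only stratification factor. The planned analyses match the design. This stands in full.
- *Continuity.* The value 2.6 allows for mortality testing since May 2007 and annual interim analyses. Any further monitoring would extend the earlier scheme. Changing the final statistic would break that sequence. This stands for mortality, although SAP 4.1 says total mortality was not formally monitored.
- *Timing.* The DSE excess of about 40 deaths is already known, and SAP 4.1 already corrects for having picked a promising trend. Choosing covariates for the formal test now adds discretion to the outcome being protected. This stands, softened because the three factors are already named in the SAP.
- *Estimand.* The adjusted HR is conditional on the covariates and differs from the site-only HR. This stands.

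A reader might infer from all this that power is being thrown away for nothing, or that the site-only HR is biased. The documents support neither. The mortality model has a stated purpose, and attenuation here reflects two different quantities, not a faulty test. Nor do the documents show that these factors are strongly prognostic; that is plausible for mortality in a cohort aged 45-76 at entry, but it is an assumption.

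These objections do not carry over to costs. Adjustment in a linear model leaves the target unchanged. SAP 4.1 makes no correction for selected trends in costs, because the hypothesis uses post-intervention data only.

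**Conclusion.** This is an efficiency point, not an error. Both co-primary analyses forgo baseline covariates that are already held.

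For costs the case for adjustment is straightforward. The size depends wholly on R²: at an assumed 5%-15%, the detectable difference falls by about $14 to $43 per year (549 − 535; 549 − 506), and power at $595 rises by about 2 to 5 points.

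For mortality the gain is modest and depends on assumed prognostic effects; the upper end needs the strongest set tested. No scenario showed a loss. Replacing the formal mortality test would be a trade-off, and the gain is not large enough to require it. Naming an adjusted analysis in advance is worthwhile, since section 4.3 otherwise leaves the choice of covariates open.

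**What to change.** 1. **SAP 5.2 and protocol 1.5 (costs).** Add baseline age (continuous), sex and CVD history to the weighted analysis of covariance. Keep the clinic-only model as a sensitivity analysis.
2. **SAP 5.1 and protocol 1.5 (mortality).** Pre-specify a site-stratified Cox model with the same three covariates, as a named analysis reported beside the site-only model. Fix it before further by-arm mortality data are reviewed. The site-only model can stay the formal test at 2.6.
3. State in 5.1 which model carries the formal test and that the two HRs estimate different quantities.

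The cost is SAP and protocol wording; no new data are needed. The downsides are that the adjusted HR is not directly comparable with the earlier cardiovascular model, and that the covariates are fixed after interim deaths by arm were known. Both should be disclosed, and both HRs reported.
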